Normal cerebral activity is composed of oscillatory activity across a wide range of frequencies, with oscillatory activity in the 30-80 Hz range known as “gamma” activity. A consistent finding in patients with AD is a relative attenuation of such faster frequencies (Babiloni et al., 2015), and dysregulation of gamma activity linked to pathologic network hyperexcitability which is also seen in animal models of AD (Verret et al., 2012). More recently, a seminal study found that exogenously-induced 40 Hz gamma oscillations reduce A β levels and amyloid plaques, and may also reduce tau levels, as seen in a mouse model of AD (Iaccarino et al., Nature 2016). The same authors have also determined that in presymptomatic AD mice, induction of gamma activity remarkably prevents subsequent neurodegeneration and behavioral deficits, suggesting that gamma induction may represent a novel and powerful therapeutic approach for AD. This opens to the possibility of modulating gamma activity in humans, potentially leading to the same beneficial effects observed in mouse models. Work from our center has recently shown the possibility of modulating brain oscillatory patterns in AD patients, with changes in brain connectivity in the gamma band (measured with EEG) observed after administration of antiepileptic drugs (Musaeus, Shafi, Santarnecchi, Herman, & Press, 2017).

That being said, drug-based interventions do not allow for precise targeting of A β deposition, while the induction of 40Hz oscillations by means of visual and/or auditory stimulations (as those implemented in the aforementioned animal model by Iaccarino et al. 2016) are limited by the nature of the stimulation, i.e. they only affect visual and auditory cortices. PET imaging allows for characterization of individual patterns of A β deposition (see Figure 2), which might be present in various cortical sites not necessarily matching the regions of action of sensorial stimulation approaches. The present proposal will leverage current knowledge on transcranial electrical stimulation to collect preliminary data on an individualized intervention to reduce A β with greater spatial accuracy, by means of transcranial alternating current stimulation (tACS).

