If abnormal results are found from the LP, a neurologist on the study in the Berenson-Allen Center will review the results. The neurologist will determine if the finding is in need of clinical follow-up. If this is the case, the neurologist will speak with the participant, will provide a letter describing the findings and need for follow-up and will be available to speak with the participant's provider if they participant agrees and gives permission to do so.

tACS visits (visits 5-14)

Study visits 5-14 will be conducted in the Berenson-Allen Center for Noninvasive Brain Stimulation at BIDMC. Participants will undergo 10 days (weekdays) of tACS. Participants will be allowed to miss one visit for a total of 9 days of tACS. If they miss more than one visit, additional sessions will be added on if it is within a reasonable timeframe as determined by the investigator, in order to reach a total of 9 sessions. Each session will consist of the following:

- Review of tACS side effects and adverse events will be completed daily before and after stimulation. An assessment of any changes in medication or medical history will be assessed on a daily basis.
- Set up for EEG and tACS which includes cleaning the scalp with alcohol, placing a cap with electrodes on the participant's head and applying gel underneath electrodes
- Three minutes of eyes-closed and eyes-open resting state EEG
- 1 hour of 40Hz tACS stimulation to targeted brain regions
 - Additionally, EEG will be recorded throughout the tACS stimulation
- Cognitive assessment (MoCA) will be completed daily to monitor any cognitive changes. If the score drops by 4 points or more, the covering neurologist will be alerted to assess the participant further. The following day, the patients will repeat a MoCA and if the score has not improved they will be reassessed by the neurologist and the participant will not receive stimulation.
- Subjects will be queried each day about their experience and how they are doing. If participants or their family members express that the participant is having difficulty, study staff will work with them to reduce any burden if possible (e.g. arranging reliable transportation, assuring that they have a snack if needed.....).

Follow Up Visit (Visits 15-18)

The following will occur at the follow up visit within approximately 1 week after the completion of the tACS study visits:

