careful monitoring of all these variables, via e.g. baseline EEG measurements, genetic data, structural and functional MRI data. Additionally, in order to estimate the likelihood of induction of gamma in each participant, a shorter tACS-EEG session will be carried out to see how each participant's brain responds to brief tACS bursts. The immediate response (e.g. increase/decrease of gamma power) after short tACS stimulation blocks (up to 20 minutes) will be collected via EEG recording before/during/after tACS. Such response will be then used to predict the response to the full tACS intervention (10 daily 1 hour sessions). Specifically, tACS will be applied to up to 4 brain regions for each brain hemisphere, including a Sham stimulation block. Stimulation intensity will not exceed limits suggested by tCS safety guidelines, equal to 2mA per stimulation electrode and 4mA total injected current across all stimulating electrodes. At the beginning of the visit (i.e. before any of the tACS stimulation blocks), the individual threshold for perception of phosphenes induced by tACS will be also estimated. Moreover, in order to collect information about brain's ability to evoke gamma activity in response to stimuli different than tACS, we will monitor the amount of gamma activity induced by brief cognitive tasks delivered using a regular desktop PC connected to the EEG system. Participants will be asked to observe images on the screen or perform basic operations, e.g. press a button when a stimulus appear, which have been shown to elicit a gamma response in humans in previous studies. The tasks will take no more than 20 minutes total. Importantly, the daily exposure to tACS could induce a beneficial change in the way participant's brain respond to tACS (i.e. increase in the individual responsiveness to gamma stimulation), which could increase the effectiveness of repeated tACS treatment cycles. To quantify this change, the same tACS-EEG recording session described above will be repeated at the end of the protocol.

Saliva Sample for DNA and Tau

Three saliva samples will be collected. One sample for tau protein and two optional samples for APOE and BDNF genotyping. Saliva samples will be collected in the Clinical Research Center and/or the Berenson-Allen Center and batch shipped to an outside laboratory for analysis.

Lumbar Puncture (optional) – CSF Biomarkers

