and stored for future analysis of putative biomarkers. Local analysis of CSF will be done at LabCorp and will include cell count, glucose, and protein.

Blood Draw

The blood draw will be completed at baseline and follow-up for testing of the same biomarkers as tested in the CSF, such as, Aβ₄₂, Aβ₄₀, total tau, phospho-tau181, cytokines, YKL-40, and BDNF. These results will be used to correlate with the CSF results. In addition, if a patient opts not to undergo the lumbar puncture, the blood tests for biomarkers will provide valuable information. Blood draws will be collected in the Cognitive Neurology Unit or in the Clinical Research Center. A maximum of 20mL (approximately 10mL for the biomarkers and 10mL for CBC, glucose, and protein) will be collected and processed by the Clinical Research Center laboratory. If the participant has an LP, blood will be sent to LabCorp for a CBC with differential, glucose, and protein to correlate with the LP analysis for any abnormalities/possible incidental findings. The remainder will be frozen, and later batch-shipped to an outside laboratory for processing. Assays will be performed by the central biomarker laboratory. Blood samples will also be frozen and stored for future analysis of putative biomarkers.

tACS (Starstim Device)

tACS will be administered using a 32-channel device. The tACS will be applied daily for 60 minutes for 10 consecutive weekdays. The Starstim is also capable of recording EEG. Five minutes of eyes-closed and eyes-open resting state EEG will also be recorded before and after each stimulation session, to assess the degree of entrainment of gamma oscillations during each tACS stimulation session.

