tACS involves the administration of low-amplitude (< 2mA) sinusoidal electrical currents via scalp electrodes. Current will be applied in the gamma frequency (40 Hz) range to the regions of tracer uptake on the amyloid PET scan on a case-by-case basis. Although tACS is usually administered via bipolar montages using two large electrodes, such montages have poor spatial specificity. Our group has been at the forefront of efforts using multifocal (multielectrode) montages that can deliver higher amplitude and more spatially specific stimulation patterns (Ruffini, Fox, Ripolles, Miranda, & Pascual-Leone, 2014). Consequently, stimulation will be applied to the target region with maximum amyloid levels using individualized multifocal (multielectrode) montages to maximize the induced electrical current in the target region.

Stimulation will be slowly ramped up/down at the beginning/end of each stimulation session to minimize skin sensation. tACS can elicit phosphenes - a sensation of light caused by excitation of the retina by mechanical or electrical means rather than by light. Participants will be queried each day at the end of the visit to see if they experienced phosphenes. They will be informed that this may happen and will be informed that they are free to ask to stop participation if the phosphenes bother them. We anticipate that a low percent of participants will experience this sensation (10%).

B. Statistical Considerations

Sample Size Justification: Given the intrinsic difficulties in the care of AD patients and the commitment required by the multi-day tACS intervention, we expect an attrition rate higher than 20%, potentially close to 30%. We will compare individual changes in amyloid according to the aforementioned SUVR threshold. In order to get valuable pilot data about changes in PET markers, we aim to recruit up to 20 participants to account for attrition with 10 expected to enroll in the study. This would allow for a final sample of 5/6 fully characterized participants who will complete the tACS

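### Resting EEG taken either side of a tACS session measures a gamma after-effect, not entrainment during the session, and should be labelled and scheduled as such

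*Combined protocol and SAP*

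**What the plan says.** **Daily sessions, tACS (Starstim Device).** "Five minutes of eyes-closed and eyes-open resting state EEG will also be recorded before and after each stimulation session", and the stated purpose is "to assess the degree of entrainment of gamma oscillations during each tACS stimulation session".

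**Daily sessions, tACS visits (visits 5-14).** The visit list gives three minutes of resting EEG, placed ahead of "1 hour of 40Hz tACS stimulation to targeted brain regions". It then adds: "Additionally, EEG will be recorded throughout the tACS stimulation". It lists no resting EEG after stimulation and gives the recording made during stimulation no purpose or analysis.

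**Study Visit Schedule.** As extracted, resting-state EEG is marked at screening only.

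**tACS-EEG registration.** In this separate session the immediate gamma response "after short tACS stimulation blocks (up to 20 minutes) will be collected via EEG recording before/during/after tACS". It is then used to predict response to the full course. The session includes a sham block and is repeated at the end of the protocol.

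**Analysis.** Data Analysis tests changes in EEG metrics, gamma spectral power among them, by paired t-test at p < 0.05. The TMS-EEG and tACS-EEG analysis paragraph computes connectivity on eyes-closed resting EEG, with segments taken on either side of rTMS and tACS.

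**Artefacts.** The only artefact removal described is for eye, jaw and forehead movement, in the TMS-EEG session. Nothing addresses the stimulation current.

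**The concern.** The quantity named and the recording assigned to it belong to different time windows. Entrainment is something the brain does while the current flows; the recordings assigned to it are made when no current flows. Their difference is an after-effect, and the two can separate in either direction. Entrainment may stop with the current. Gamma power may also differ after an hour in the chair for other reasons, such as drowsiness or muscle tension, and the daily sessions list no sham condition to absorb these.

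At stake is the trial's mechanistic reading. 40 Hz entrainment is the proposed route from stimulation to amyloid change, and gamma spectral power is one of the responses named in Exploratory Aim 1. Under the present label, a flat before/after result invites the conclusion that stimulation did not engage the target, and a positive one invites the conclusion that it did. The contrast supports neither.

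A secondary matter is the EEG recorded during stimulation. It is the only recording in the right window, so it is the natural place to turn for an entrainment claim. It also contains the injected signal at the outcome frequency.

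**Working it through.** The plan gives no figure to reproduce here. The main check is of the text; the arithmetic only illustrates it.

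**1. Quantity against recording**

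| Place | EEG recorded | What it is said to show |
|---|---|---|
| tACS (Starstim Device) | 5 min rest, pre- and post-session | entrainment during the session |
| tACS visits (5-14) | 3 min rest, listed ahead of stimulation; EEG throughout stimulation | nothing stated |
| Study Visit Schedule | resting EEG at screening only | nothing stated |
| tACS-EEG registration | before, during and after short blocks | immediate response after the blocks |

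The first row assigns stimulation-free EEG to a during-stimulation quantity. The first three rows also disagree on duration and on whether any post-session resting EEG is taken.

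**2. How far the two quantities can separate**

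All amplitudes here are assumptions, because the documents give none. The simulation used 300 s of EEG sampled at 500 Hz, white noise with SD 5 µV, 4 s Hann windows, and power summed over 38-42 Hz.

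- Entrainment of 2 µV during stimulation, no after-effect: during/pre = 5.65, post/pre = 1.06.
- No entrainment, after-effect of 2 µV: post/pre = 6.20.

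Hand check: a 4 s window has N = 2000 samples and 17 frequency bins in 38-42 Hz. The expected ratio for a sinusoid of amplitude a in noise of SD σ is 1 + N·a²/(4·17·σ²) = 1 + 2000·4/(4·17·25) = 5.71. In 200 repeats the ratio with the sinusoid present averaged 5.74 (95% of values 5.29 to 6.32), and the ratio with none averaged 1.01 (0.89 to 1.12). So 5.65 and 6.20 are the same result within sampling noise, and 1.06 is no change. The before/after contrast misses entrainment in the first case and suggests it in the second.

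**3. Whether the during-stimulation EEG fills the gap**

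The protocol describes the stimulation thus: "tACS involves the administration of low-amplitude (< 2mA) sinusoidal electrical currents via scalp electrodes", at 40 Hz. Section B2 defines the band of interest: "with oscillatory activity in the 30-80 Hz range known as “gamma” activity". The injected frequency therefore lies inside the outcome band. Its size at the recording electrodes is not given, so assume 0.1 to 10 mV of artefact against 0.5 to 1 µV of neural 40 Hz activity.

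- Amplitude ratio = artefact/neural: 100 µV / 1 µV = 100, up to 10,000 µV / 0.5 µV = 20,000.
- In decibels, 20·log10(ratio): 40 to 86 dB.
- Residual power ratio after removing 99.9% of amplitude (60 dB) = (ratio/1000)²:

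| Artefact | Neural 1 µV | Neural 0.5 µV |
|---|---|---|
| 0.1 mV | 0.01 | 0.04 |
| 1 mV | 1 | 4 |
| 10 mV | 100 | 400 |

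The range runs from negligible to overwhelming. It does not show that the recording is useless; it shows that its value depends wholly on an artefact level and a removal method that the plan does not state.

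**4. The tACS-EEG predictor**

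The sentence describes the response as the one following the blocks. The words before/during/after list when EEG is collected. Nothing says which segments enter the predictor. The sham block can serve as comparator for an after-minus-before measure. If it delivers little or no sustained 40 Hz current (the protocol does not describe it), it cannot do so for during-block EEG, because active minus sham would retain the artefact.

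**The case against.** The best defence is that post-stimulation EEG is a reasoned proxy. Section B2 cites tACS effects lasting up to 70 minutes and long-lasting gamma power changes after temporal-lobe stimulation, and Aim 3 concerns resting-state EEG, for which stimulation-free recordings are right. This stands as a reason to measure an after-effect. It does not turn an after-effect into a degree of entrainment, and the title of the 70-minute source refers to alpha-frequency tACS, not 40 Hz.

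The defence is also right that no sample size, decision rule or primary conclusion rests on this measure, and that gamma is not the only evidence of engagement: the Lumbar Puncture section names a fall in CSF tau as a signal of target engagement.

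A reader might go further and infer that the plan will read a 40 Hz rise during stimulation as a brain response, or rank patients as responders partly on artefact. The documents do not support that. The visit list gives the during-stimulation EEG no analysis, the tACS-EEG section describes a response after the blocks, and the connectivity metrics use resting segments on either side of stimulation. Nor do the documents show that EEG recorded during tACS could never be used.

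**Conclusion.** The point holds for the daily-session EEG: followed as written, the plan would report an after-effect under the name of entrainment during stimulation. This follows from the text alone and needs no assumed amplitude. The simulated ratios show only that the error can run either way.

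For the EEG recorded during stimulation the conclusion is narrower. The injected current sits at 40 Hz within the outcome band and no method for removing it is given, so as the plan stands that recording cannot support a 40 Hz claim. The residual range of 0.01 to 400 times neural power rests on assumed artefact size, neural amplitude and suppression, and is not an estimate for this trial. Which segments enter the tACS-EEG predictor is unclear rather than wrong.

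The change is worth making because it alters what the trial can conclude about mechanism at very small cost. It does not touch the PET or safety results.

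**What to change.** 1. In tACS (Starstim Device), replace the reference to entrainment during each session with *after-effect on gamma power following each session*, and limit the conclusion to that.
2. Reconcile that section, the tACS visits (visits 5-14) list and the Study Visit Schedule, so that the post-session resting EEG is scheduled and has one stated duration. Item 1 depends on this recording.
3. In tACS-EEG registration, state that the predictor is computed from stimulation-free segments, after minus before, compared with the sham block.
4. State that EEG recorded during tACS will not support 40 Hz power, coherence or phase claims unless a stimulation-artefact method and a control condition are specified in advance. It can still be recorded for monitoring.

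Cost: wording, plus a short recording per session if the post-session EEG is not already being taken. If the five minutes applies to each eye condition, that is 2 × 5 = 10 minutes a session, or 100 minutes over 10 sessions; if it covers both conditions together, half that. The trial gives up a claim of online entrainment unless it takes the further step in item 4.
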